### **Markers of Innate immunity and inflammation**

Markers of Innate immunity and inflammation will be measured at baseline, and weeks 12, 48, and 96.

For participants recruited in Melbourne only: A panel of innate immune markers selected from HaCH including monocyte markers (CD14, CD16) of activation (CD38), of expression linked to migration, adhesion and progression of atherosclerotic plaque (CD11b, CX3CR1) will be performed.

In participants from both sites in plasma, markers of inflammation (IL6, sCD163) and monocyte activation / chemokine ligands (sCD14, neopterin, CCL2), S-VCAM-1 and adinopectin will be measured.

High sensitivity C-reactive protein (hsCRP) will be performed by the AH laboratory according to standard protocols

### **Stored Samples**

4ml of plasma will be stored indefinitely for possible future testing and research for participants that give their consent. Storage samples will be collected at baseline and weeks 12, 48 and 96.

Samples will be stored at -80°C in the Burnet research laboratory and -80°C at the Swiss sites. Swiss sites will transfer the samples to the HUG central “sérothèque” for storage. Participants recruited from the Alfred Hospital will also have PBMC’s stored at -140 in the Burnet research laboratory.

## **11.3 Carotid IMT**

The bilateral carotid artery will be assessed for cIMT by B Mode ultrasound using a Philips iE33 with 11 MHz linear transducer (Melbourne). The Swiss sites will be using the ultrasound machine tested and accepted by the core lab in Montréal following the Standard Operating Procedures for cIMT. The cIMT measurement is a painless and harmless non-invasive ultrasound procedure performed on patients’ left and right common carotid arteries. The procedure takes 20 minutes to perform. The cIMT defined as the distance between lumen-intima interface and media-adventia interface is measured from the 2D high resolution digital images obtained using an automated border-detection algorithm. cIMT will be

determined on areas identified as without plaque by 12 consecutive measurements made 1-3 cm proximal to the carotid bulb, but the presence of plaques will be noted. All measurements will be performed in duplicate, by the same operator at the AH Heart Centre or the Swiss site, who will remain blinded to participant randomization, throughout the study.

Investigators and patients will not receive results from cIMT (or cPWV – see below) until the end of the study, unless a significant carotid plaque warranting further investigation and management is identified. Patients who are identified as having a significant plaque will be withdrawn from the study and referred to a cardiologist at the AH or the Swiss site for further assessment and management as necessary.

### 11.4 Pulse Wave Velocity

Australian site only: cPWV will be determined using simultaneous applanation tonometry of the carotid and femoral arteries. PWV will be calculated as manubrium sternum-to-femoral artery distance minus carotid artery-to-manubrium sternum distance divided by the time interval between the carotid and femoral pulses calculated from the upstroke of the systolic waveform (maximum of the second derivative). The cPWV will be reported as the average of pulse waves recorded over a 10 second period. It is a painless and harmless procedure that takes 20 min to perform by trained operators. The co-efficient of variation for this measurement is 5%.

## 12 Visit Schedule

### 12.1 Screening

The screening procedures will be completed in one visit at the study site.

Participants will present to the study site, having fasted from overnight for at least 12 hours (no food, caffeine or caloric drink; free water is encouraged).

Written informed consent will be obtained at screening visit by trained research staff (see Appendix 22.5 and 22.6). Participants will be informed in written and orally prior to the screening visit and given sufficient time for reflexion before signing the consent form.

#### Assessments

1. Demographic data, medical history and medication questionnaire to be completed
2. Full physical examination including:
  - a. Height and weight
  - b. Assessment of peripheral pulses
  - c. Blood pressure
  - d. ECG
3. Laboratory assessments
  - a. FBE and biochemistry
  - b. Beta HCG for all women of child bearing potential
  - c. Fasting metabolic assessment
  - d. HIV viral load and CD4+ T cell count (and percentage)
4. Structural assessments
  - a. cIMT
  - b. cPWV (\*Melbourne Participants only)
5. Calculations
  - a. BMI

- b. Creatinine clearance
- c. FRS
- d. D.A.D. risk score

### 12.1.1 Eligibility

Clinical eligibility will be recorded based on the inclusion (1-6) and exclusion criteria (7-26) listed below.

### 12.2 Inclusion Criteria

1. Provision of written, informed consent
2. Age >30 years
3. Moderate coronary heart Disease (CHD) risk, defined as FRS of 10-15%1
4. HIV positive
5. Stable ARV regimen > 3 months (i.e. no recent drug change [changes in dosages are accepted])
6. Plasma HIV viral load <200copies/ml for  $\geq$  6 months

### 12.3 Exclusion criteria

7. Recommended use of lipid lowering drug therapy according to Australian Guidelines (National heart foundation 2012)2
8. Family History of myocardial infarction or stroke in a male first degree relative before 55 years of age, or a female first degree relative before 65 years of age
9. Type 2 Diabetes
10. Familial hypercholesterolemia
11. Aboriginal or Torres Strait Islander people with LDL-C >2.5 mmol/L
12. Blood pressure  $\geq$  180/110
13. Documented history of:
  - a) Ischemic stroke or transient ischemic attack (TIA)
  - b) Peripheral arterial disease (regardless of severity)
  - c) Congestive heart failure
  - d) Coronary artery disease or ECG findings consistent with prior MI
14. Carotid artery stenosis or >50% occlusion of the carotid artery known previously or discovered during screening procedures
15. Total Cholesterol > 7.5 mmol/L
16. Triglyceride level >4.0 mmol/L
17. HDL-c <1 and Total cholesterol > 6.5mmol/L
18. Current or prior (last 6 months) statin therapy
19. Current or prior (last 6 months) use of ezetimibe
20. Current or prior (last 6 months) use of fibrates or niacin
21. Contraindication to statin use
  - f. Pregnancy or lactation
  - g. Hypersensitivity to statins
  - h. Known myopathy or baseline CK > 3x ULN
  - i. Contraindicated concurrent medication
  - j. Current cyclosporine, fusidic acid or oral corticosteroid use

22. Concomitant antiplatelet drug (Aspirin, Abciximab, Anagrelide, Cilostazol, Clopidogrel, Dipyridamole, Eptifibatide, Ticagrelor, Ticlopidine, Tirofiban, Terutroban)
23. Unable to complete study procedures (i.e. attendance at AH for cIMT and cPWV testing or cIMT images not accepted for analysis despite redo examination)
24. Any active, clinically significant disease (including but not limited to; pancreatitis, significant psychiatric disorders, acquired immunodeficiency syndrome (AIDS) defining illnesses) which may impact on the results of the study, increase the risk of serious adverse events (SAE) or limit participants life expectancy to < 24 months,
25. Any active, clinically significant disease (including but not limited to; pancreatitis, significant psychiatric disorders, acquired immunodeficiency syndrome (AIDS) defining illnesses) which may impact on the results of the study, increase the risk of serious adverse events (SAE) or limit participants life expectancy to < 24 months
26. Concomitant renal or hepatic disease, defined as the presence of the following:
  - a. Creatinine clearance <50 ml/min (calculated using the Cockcroft-Gault equation)
  - b. Transaminase (ALT, AST) above 3 times upper normal limit
  - c. Acute hepatic failure
  - d. Compensated cirrhosis Child Class B or C

If the patient fulfils all eligibility criteria (1-26 above) then a baseline visit will be booked. CRFs from participants assessed but found to be ineligible for inclusion in the study will be entered into the database recording the reason for ineligibility.

#### **12.4 Randomisation**

Patients will be block randomised in a 1:1 ratio to receive rosuvastatin or placebo. Randomisation will be stratified by centre.

#### **12.5 Baseline visit**

Participants will be required to present to the study site having fasted overnight for at least 12 hours (no food, caffeine or caloric drinks; free water is encouraged)

Assessments performed:

1. Targeted physical examination and updated history, assessment for new concomitant medications
2. Adverse event assessment
3. Laboratory assessments
  - a. Biochemistry
  - b. Fasting metabolic assessment
  - c. hsCRP
  - d. Markers of innate immunity and inflammation
  - e. Storage of plasma and PBMCs (\*Melbourne participants only) for possible further analysis in the future

Patients will be provided with a three (3) month supply of the study medication and educated regarding possible clinical signs of potential adverse events (muscle ache, fever, abdominal pain, jaundice, rash); regardless of randomisation. Patients will also be provided with contact details for study co-ordinators in case of adverse event.

### 12.6 Week 12 visit

Participants will be required to present to the study site having fasted overnight for at least 12 hours (no food, caffeine or caloric drinks; free water is encouraged)

Assessments performed:

1. Assessment for adverse events
2. Laboratory assessment for:
  - a. FBE
  - b. Biochemistry
  - c. hsCRP
  - d. Markers of innate immunity and inflammation
  - e. HIV Viral load and CD4+ T-cell count (and percentage)
3. Storage of plasma and PBMCs (\*Melbourne participants only) for possible future analysis

Patients provided with a further three (3) month supply of the study medication.

### 12.7 Week 24 visit

Participants will be required to present having fasted overnight for at least 12 hours (no food, caffeine or caloric drinks; free water is encouraged)

Assessments performed:

1. Assessment for adverse events
2. Laboratory assessment for:
  - a. Biochemistry
  - b. Fasting metabolic assessment
  - c. HIV Viral load and CD4+ T-cell count (and percentage)

Patients will be provided with a six (6) month supply of the study medication

### 12.8 Week 48 visit

Participants will be required to present having fasted overnight for at least 12 hours (no food, caffeine or caloric drinks; free water is encouraged).

Assessments performed:

1. Targeted physical examination and updated history, assessment for new concomitant medications
2. Weight recorded
3. Compliance assessment
  - a. Self-assessment questionnaire and VAS
4. Adverse event assessment
5. Laboratory assessments
  - a. Biochemistry
  - b. Fasting metabolic assessment
  - c. HIV Viral load and CD4+ T-cell count (and percentage)
  - d. Markers of innate immunity and inflammation
  - e. Storage of plasma and PBMCs (\*Melbourne participants only) for possible further analysis in the future
6. Calculations

- a. Creatinine clearance
- b. BMI
7. Structural assessments
  - a. cIMT
  - b. cPWV (\*Melbourne participants only)

Patients will be provided with a six (6) month supply of the study medication

### **12.9 Week 72 visit**

Fasting NOT required for this visit

Assessments performed:

1. Assessment for adverse events
2. Laboratory assessment for:
  - a. Biochemistry
  - b. HIV Viral load and CD4+ T-cell count (and percentage)

Patients will be provided with a six (6) month supply of the study medication

### **12.10 Week 96 visit**

Participants will be required to present to the AH having fasted overnight for at least 12 hours (no food, caffeine or caloric drinks; free water is encouraged).

Assessments performed:

1. Targeted physical examination and updated history, assessment for new concomitant medications
2. Weight recorded
3. Compliance assessment
  - a. Self-assessment questionnaire and VAS
4. Adverse event assessment
5. Laboratory assessments
  - a. FBE
  - b. Biochemistry
  - c. Fasting metabolic assessment
  - d. hsCRP
  - e. HIV Viral load and CD4+ T-cell count (and percentage)
  - f. Markers of innate immunity and inflammation
  - g. Storage of plasma and PBMCs (\*Melbourne participants only) for possible further analysis in the future
6. Calculations
  - a. Creatinine clearance
  - b. BMI
7. Structural assessments
  - a. cIMT
  - b. cPWV (\*Melbourne participants only)

Patients will be advised to cease study medication. Statin will be prescribed according to physician's assessment.

### **12.11 Unscheduled visits**

Unscheduled visits may be initiated by study co-ordinators and doctors, participants or treating physicians. All assessments made during unscheduled visits will be recorded on the CRF.

This visit may involve, but is not limited to, the following assessments; targeted medical review and physical examination, additional laboratory examination for safety reasons. SAE or AE visits may occur as unscheduled visits.

### **12.1 Withdrawal visit**

For participants that fulfil any of the withdrawal criteria above a withdrawal visit is performed if the participant agrees. All assessments made during the withdrawal visit can be recorded on the CRF (unscheduled visit). This visit will include, but is not limited to, a targeted medical review and physical examination, laboratory examination for safety reasons (chemistry and haematology), pregnancy test for women and study drug return. Tests performed can vary according to the judgement of the study physician.

Clinical or biological abnormalities perceived at the withdrawal visit will be followed at an interval decided by the study physician, until they are resolved or baseline values obtained.

Participants that withdraw from the study may be contacted by telephone at study end for vital status, unless they refuse and this is documented.

In Australia: In the event of withdrawal of consent by the participant, the Form for withdrawal of participants is completed.

### **12.2 Time windows**

The baseline visit will occur within four (4) weeks of screening to allow for laboratory assessments to be completed and FRS to be calculated confirming eligibility. Study visits at weeks 12 and 24 have a visit window of +/- 14 days (to allow for scheduling of structural assessments and subject convenience). Study visits at weeks 48, 72 and 96 have a visit window of +/- 6 weeks.

## **13 Adverse Events**

An AE is defined as follows:

Any untoward medical occurrence in a clinical investigation subject administered a medicinal product and which does not necessarily have a causal relationship with this treatment. An AE can therefore be any unfavourable and unintended sign, symptom, or disease temporally associated with the use of a medicinal product, whether or not considered related to the medicinal product.

Pre-existing or recurrent conditions that occur during the study should not be considered as AEs unless they change in frequency or severity.

All AEs that occur from the time the subject consents to participate in the study and throughout the duration of the study shall be recorded as an AE in the individuals CRF.

At the final study visit (week 96) any ongoing adverse events deemed related to study drug will be followed up for a minimum of 30 days and until resolution.

In case a treatment interruption is needed during the treatment period in the event of a suspected toxicity, the subject will not automatically be withdrawn from the trial, as long as treatment interruption does not exceed 4 weeks.

AEs and SAEs will be categorised and recorded as per the modified Division of AIDS table for grading the Severity of Adverse Events (see Appendix 22.6). Causal relationship of AEs and SAEs to the trial and the study medication will also be assessed.

## 14 Serious Adverse Events

A serious adverse event (SAE) is defined as follows:

Any adverse drug experience occurring at any dose that results in any of the following outcomes:

- Death
- Life-threatening situation (subject is at immediate risk of death)
- In-patient hospitalisation or prolongation of existing hospitalisation
- Persistent or significant disability/incapacity
- Congenital anomaly/birth defect in the offspring of a subject who received the study drug
- Other medically significant events that may not be immediately life-threatening or result in death or hospitalization, but based upon appropriate medical and scientific judgement, may jeopardize the subject or may require medical or surgical intervention to prevent one of the outcomes listed above.

### 14.1 Serious Adverse Event Reporting Requirements

The Principal Investigator and/or the project coordinator (coordinating center for Swiss sites) must be notified immediately (within 24 hrs of awareness of the event) regarding the occurrence of any SAEs.

The Principal Investigator and/or the study monitor (coordinating center for Switzerland) will report any SAE that fulfils the criteria for expedited reporting (unexpected and drug related events) to the appropriate regulatory authorities within the required reporting time frame. SAEs must also be reported to the approving ethics committee(s) as required by the ethics committee reporting procedures.

SAEs must be reported during a subject's participation in the study (whether receiving study medication or not) or within 30 days of receiving the last dose of study agent, whichever is longer.

Any SAE that is ongoing at the final study visit (week 96) will be followed until resolution or stabilisation (for those events that will not resolve).

*For Switzerland: Safety reporting will be performed according to regulatory requirements detailed in the Overview of safety reporting procedures that is published on the Swissethics (Swiss association of Ethics Committees for clinical trials) website:*

*[http://www.swissethics.ch/doc/templates/Overview\\_safety\\_AGEK\\_dec11\\_final.pdf](http://www.swissethics.ch/doc/templates/Overview_safety_AGEK_dec11_final.pdf).*

*The coordinating centre Geneva must be reported to immediately by the study site in case of an SAE or SUSAR. The coordinating centre Geneva will report all drug related events (Adverse Drug Reactions) to Swissmedic in an annual update safety report. All SUSARS/SUSADRs (Suspected, unexpected Serious Adverse Drug Reaction) will be reported*

*to Swissmedic within 7 days for fatal and/or life threatening ADRs, 15 days for all other reportable ADRs.*

## 15 Data safety and monitoring board

An independent Data safety and monitoring board (DSMB) will be set up to monitor the safety of and efficacy in the participants enrolled in the trial. The DSMB will be chaired by [name]. Members will include one cardiologist from Switzerland (Proposition: [name]), one methodologist (Proposition: [name]), and one statistician from Australia (Proposition: [name]).

Data will be sent to the DSMB every 24 weeks. A summary of SAEs, grade 3/4 AEs and laboratory toxicities, and AEs leading to discontinuation will be provided on a monthly basis.

There will be a single, un-blinded, interim safety and efficacy analysis and review meeting after the last participants has completed 48 weeks of follow-up. The following data will be reviewed:

### Safety data:

- Participant recruitment, accrual, retention, and withdrawal information
- Adverse events (AEs) and serious adverse events (SAEs)
- Clinical test results and laboratory values
- Vital signs and physical exam outcomes
- Participant questionnaires
- Study drug dose information
- Any other safety-supporting data requested by the DSMB

### Efficacy data

- cIMT data (primary endpoint measure)

Primary outcome measures (cIMT) and the first secondary outcome measure (adverse effects) will be analysed. Based on these analyses, the DSMB will make recommendations regarding the continuation, modification or termination of the trial.

### Stopping rules:

The DSMB may recommend stopping of the trial for the following reasons:

- The data show a significantly increased risk of serious adverse effects in one of the treatment groups.
- On the basis of a positive efficacy result only when the data are truly compelling and the risk of a false positive conclusion is acceptably low. The trial will only be stopped for positive efficacy if a strong statistically and clinically significant difference in cIMT is seen between treatment arms.
- If interim data suggest that the product under study is of no benefit (no trend indicating superiority of the product), or that accrual rates are too low and/or that noncompliance is too great to provide adequate power for identifying the specified benefit, the DSMB may consider whether continuation of the study is futile and may recommend termination on this basis.

- It becomes clear that successful completion of the study is not feasible (e.g. there is an excess of patient dropout, missing data, lack of recruitment etc).

The DSMB may recommend modifications to individual stopping rules if additional safety concerns arise during from their continuing reviews of the study data.

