#### 6.6 Sample size

The METEOR study of rosuvastatin in HIV negative participants with low to intermediate CVD risk found a mean Common Carotid Artery cIMT progression rate of 0.0088 mm/2 years in the placebo arm and 0.0004mm/2 years in the rosuvastatin arm^22, giving an effect size of 0.0084 mm/2 years (95% relative reduction) with a standard deviation (SD) of 0.033 mm/year. A pilot study in HIV positive patients at the AH (n=10) found that in participants treated with non-nucleoside reverse transcriptase inhibitors (the most common cART regimen), the mean cIMT progression rate was 0.04 mm/year with a SD of 0.0782 mm (personal communication [name], Baker IDI), similar to estimated values proposed for cIMT progression in HIV positive participants at low to intermediate CVD risk (mean 0.045 mm/year, SD 0.08 mm; 62).

Conservatively assuming a cIMT progression rate of 0.080 mm with a SD of 0.09 mm over 2 years and near stabilisation of cIMT (95% relative reduction) with rosuvastatin, we can assume an effect size of 0.076 mm with a SD of 0.09 mm. Sample size was calculated using an independent groups t-test with an alpha threshold of 1% and a power of 90%. Based on these hypotheses, with 44 participants in each group this study will be able to detect an effect

size of 0.076 mm with a SD of 0.09 mm over 2 years between the 2 groups. With an estimated 15% total drop-out rate over 96 weeks, we estimate that a total study population of 102 will be required.

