An interim analysis will be performed at 48 weeks. The final analysis at 96 weeks will be conducted when all patients will have completed the follow-up visits or have been permanently lost to follow-up, and the study database is signed off as checked and complete.

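### The unblinded interim test of cIMT allows a stop for efficacy with no stated boundary or adjusted final level, so the 1% error rate is not guaranteed

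*Combined protocol and SAP*

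**What the plan says.** Section 15 of the combined protocol and SAP provides for a single unblinded look at safety and efficacy once the last participant has completed 48 weeks. Under its efficacy data heading, cIMT is named as the primary endpoint measure, and "Primary outcome measures (cIMT) and the first secondary outcome measure (adverse effects) will be analysed". The DSMB may then recommend continuing, modifying or ending the trial.

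The stopping rules in Section 15 allow a stop for positive efficacy when the data are convincing enough and the false-positive risk is low enough to accept. They add: "The trial will only be stopped for positive efficacy if a strong statistically and clinically significant difference in cIMT is seen between treatment arms". No p-value, boundary or spending function follows.

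Section 17 adds only the timing: "An interim analysis will be performed at 48 weeks". It states no significance level for the primary test. The one level it names, 1%, belongs to a chi-square comparison of missing IMT measurements.

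The 1% for the treatment comparison appears only in Section 6.6, which sizes the trial with an independent groups t-test at "an alpha threshold of 1% and a power of 90"%. It makes no allowance for an interim look.

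**The concern.** The plan gives the primary endpoint two chances to produce a positive claim: once at the interim, if the DSMB stops for efficacy, and once at week 96. The sample size calculation gives the whole 1% to the second. Whatever chance of a false positive the interim carries is then added to that 1%, less the overlap between the two looks.

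The verbal conditions cannot be turned into an error rate. One DSMB could act at p=0.01 and another at p=0.0001, and both could say that they had followed Section 15. A reader of the final result could not then say what its false-positive rate was. A boundary chosen after the unblinded data have been seen would not repair this.

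The interim comparison is also not defined. Section 15 names cIMT but no contrast, model or summary. Section 17 makes the change to week 96 primary and the change to week 48 secondary. For both, it leaves open whether mean or maximal IMT is used and which covariates enter the model.

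**Working it through.** **Inputs from the documents.** Section 6.6: difference 0.076 mm, SD 0.09 mm, 44 evaluable per group, alpha 1%, power 90%, t-test. Section 15: one interim efficacy look, with a stop for positive efficacy only. Neither the sidedness of the test nor the interim threshold is given.

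**Assumptions.** The test is two-sided, because that reproduces the plan's own figure (step 1). The final test is at 1%, taken from Section 6.6. The interim and final statistics are bivariate normal with correlation ρ. The documents do not give ρ, so a range of 0.5 to 0.8 is shown.

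**Step 1: reproduce the sample size.** Noncentrality = (0.076/0.09) × √(44/2) = 0.844 × 4.690 = 3.961, with 86 degrees of freedom. The two-sided 1% critical value is 2.634, and the noncentral t distribution gives power 90.5%. With 43 per group the power is 89.7%, so 44 is the smallest number that reaches 90%. A one-sided 1% test would need only 38. The stated 44 is thus a two-sided, single-look figure that uses the full 1%.

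**Step 2: overall error with two looks.** Let p1 be the two-sided interim threshold, of which only the half in favour of rosuvastatin can stop the trial. Let p2 be the two-sided final level. Then

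overall error = p1/2 + p2 − P(both looks significant).

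With p2 = 0.01:

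| Interim threshold p1 | ρ | p1/2 + p2 | Overlap | Overall error |
|---|---|---|---|---|
| 0.01 | 0.5 | 0.0150 | 0.00050 | 1.45% |
| 0.01 | 0.8 | 0.0150 | 0.00169 | 1.33% |
| 0.001 | 0.5 | 0.0105 | 0.00009 | 1.04% |
| 0.001 | 0.8 | 0.0105 | 0.00033 | 1.02% |

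If a stop in either direction were counted, two looks at 1% would give 0.020 less twice the overlap: 1.90% (ρ = 0.5) to 1.66% (ρ = 0.8).

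**Step 3: levels that keep the total at 1%.** Take an interim threshold of p<0.001.

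- Final level 0.009: even with both interim tails counted, the total is at most 0.001 + 0.009 = 0.010, whatever ρ is.
- Final level 0.0095: with a benefit-only stop, the total is at most 0.0005 + 0.0095 = 0.010. After subtracting the overlap it is 0.99% (ρ = 0.5) to 0.97% (ρ = 0.8).

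**Step 4: cost in power at 44 per group.** The calculation is that of step 1 with the new critical value.

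| Final two-sided level | Critical t | Power |
|---|---|---|
| 0.01 | 2.634 | 90.5% |
| 0.0095 | 2.653 | 90.1% |
| 0.009 | 2.673 | 89.8% |

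**The case against.** The strongest reply is that Section 15 is not careless about this risk. It asks for a difference that is both statistically strong and clinically relevant, and it makes an efficacy stop conditional on an acceptably low false-positive risk. A DSMB reading this strictly might act only at p<0.001, where the excess is a few hundredths of a percentage point, or at p<0.0001, where the total is 1.00%. That stands, and it limits the size of the problem. It does not remove it, because the strictness is left to judgement at the time of the unblinded look.

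Three stronger readings are tempting, and the documents do not support them.

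- A reader might infer that the 1% is certainly exceeded by a material amount. The interim threshold is unstated, so only the lack of a guarantee follows.
- A reader might take statistical significance at the interim to mean the usual 5%, which would give 5.3% to 5.7% with both tails counted. The only significance levels in the documents are 1%, and Section 15 asks for strong evidence, so a threshold looser than the trial's own has no basis. Counting both tails also goes against a rule that stops only for positive efficacy.
- A reader might infer that an early stop would rest on the week-48 change. This is likely but not stated. The look takes place when the last participant reaches week 48, and earlier enrollees may by then have week-96 scans whose use is not excluded. Their use could also raise the correlation; at 0.9, two looks at 1% with a benefit-only stop give 1.25%.

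A boundary might be recorded elsewhere, but Sections 15 and 17 refer to none. The futility provisions are not at issue: stopping for futility does not raise the false-positive rate.

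**Conclusion.** The point holds as a gap in specification with a modest numerical consequence. An unblinded efficacy look at the primary endpoint can end the trial, no boundary governs it, and no final level is adjusted for it. The planned 1% is therefore not guaranteed.

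The plausible excess runs from almost nothing to just under half a percentage point, depending mainly on the interim threshold. This rests on the assumed correlation, a two-sided final test at 1% and a stop for benefit only. The 1% is itself partly an inference, since it is stated for the sample size and not for the primary test in Section 17.

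What data an early stop would rest on is an ambiguity to resolve and not an established fault. It matters because Section 17 lists the week-48 contrast among the secondary analyses.

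**What to change.** In Sections 15 and 17, before the unblinded look, adopt one of two options.

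1. Keep the efficacy stop. State that it requires two-sided p<0.001 in favour of rosuvastatin on a named cIMT contrast, summary measure and model. Set the final week-96 test at two-sided 0.009, which keeps the total at or below 1% for any correlation and whichever interim tails are counted. Alternatively, set it at about 0.0095, which suffices if the stop is for benefit only.
2. Drop the efficacy stop, keep the interim for safety and futility, and keep the full 1% for week 96.

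Under either option, state the level and sidedness of the primary test in Section 17. Under the first, also say whether an early stop would rest on the week-48 change, on all scans available at that time, or on another contrast.

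The cost is a few sentences and no extra participants. On the t-test used for sizing, with 44 per arm, power falls from 90.5% to 89.8% (final level 0.009) or 90.1% (0.0095), and not at all under the second option.
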